The objective of this study is to measure the structural changes that occur in the foot when wearing arch supports, and how these changes correlate with overall relief of common structural-related foot ailments; plantar fasciitis, metatarsalgia, and/or hallux valgus

Specific Aim #1:

Measure any changes that occur in the position and alignment of the foot bones relative to one another using weight bearing radiographs and weight bearing CT scans, with and without over-the-counter arch supports under the sole of the feet.

Hypothesis: Arch supports (orthoses) will alter the positioning and alignment of the bones of the foot when standing. Any changes will be measurable in three dimensions, using both weight bearing CT scans and standard anterior-posterior and lateral radiographs.

Specific Aim #2:

Demonstrate if there is a correlation between symptomatic relief of painful foot conditions including hallux valgus, pes planus, metatarsalgia, as well as low back, knee and ankle pain using validated clinical scores and quality of life measures.

Hypothesis: Painful foot conditions as well as certain types of low back, knee, and ankle pain will improve when subjects wear over-the-counter arch supports on a regular basis, as demonstrated by validated subjective scoring.

3. General Description of Study Design

This study is a single armed prospective case series designed to evaluate the efficacy of treating common structural-related foot ailments (i.e. plantar fasciitis, metatarsalgia, and/or hallux valgus) with a high quality non-custom made arch support. It is believed that these conditions are the result of inadequate or poorly fitted arch supports resulting in a lack of structural correction in the foot while weight bearing. Over-the-counter insoles are believed to counteract the shortcomings in foot structure that result in these painful conditions. In this study, it is proposed that changes in foot morphology can be measured quantitatively using weight bearing CT Scan (Computerized Tomography) and X-rays of the subject with and without the arch supports. Subjects will also answer questions from a validated series of questionnaires pertaining to their foot condition and generalized health and activity level.

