- Pre-treatment assessment to be completed on day one.
- Subjects will describe their immediate impressions without and with the arch support in place.

Insole Selection

- Based on clinical assessment, properly sized set of arch supports and properly fitted athletic shoes will be dispensed to the study subject. Fit and comfort will be confirmed before proceeding with other data collection steps.

Baseline Measurements

- Each subject will have one weight bearing CT and one weight bearing X-ray series (AP/Lateral) taken barefooted and a second series taken with the selected arch support in place. Subjects are enrolled sequentially, and there is no placebo group.
- Image analysis will compare position and alignment of bones of the foot to measure differences in positioning with and without arch supports, using CT and X-ray. X-ray measurements will include intermetatarsal angles, hallux abductus angle, sesamoid position, metatarsal declination angle, calcaneal inclination angle, talocalcaneal angle, calcaneocuboid angle, and overall morphology. CT measurements will be used to determine the 3-dimensional positioning of the foot bones, and will document the change in position that occurs with and without arch support.

Logging of Activities and Symptoms

- Study subjects will be issued a diary and they are to record the following data on a weekly basis. The diary will be sent to the patient via email and RedCap links.
 - Estimated distance walked (Those able to count steps are encouraged to do so.).
 - Activities of Daily Living
 - Symptoms, and level of pain rated on a VAS scale.
 - Compliance with wearing of insoles and athletic shoes

b. Treatment Phase

We will be conducting follow up surveys via email and RedCap links with patients.

Monthly follow up (End of weeks 4, 8, and 12)

- Confirmation of eligibility based on inclusion/ exclusion criteria
- Medical history: New or relevant changes to medical history, including history of current disease, and information regarding underlying diseases will be recorded
- Review of logged data from daily diary
- Completion of physician re-assessment and OAS and VAS scoring.
- Validated questionnaires will be completed at each of the 3 follow-up visits.
 - ACFAS Universal foot Evaluation
 - AOFAS Outcome score
 - Oswestry Low Back Disability score
 - Pain Intensity Score
 - Global Health Test
 - Pain Interference
- Record any Adverse Events

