- Clinical photographs will be taken with and without the arch support in place, while barefooted.

c. Study Completion/Termination

When the subject completes the study, voluntarily withdraws, is withdrawn for any reason, the study is terminated, or the Investigator is no longer able to locate the subject, the reason for the withdrawal will be reported along with any relevant information concerning the device, subject condition or death.

All subjects withdrawn from the study due to an adverse event, or have an adverse device effect or serious adverse event at study completion, will be followed until the adverse device effect or serious adverse event is resolved, a resolution is no longer expected or it returns to baseline.

Treatment Discontinuation

After completing the estimated 12-week visit requirements, the subject will be considered to have completed the study. In all cases of withdrawal, the date and the reason for withdrawal are to be documented.

Primary Endpoint

The primary endpoint is the change in symptoms when arch supports are worn, as compared to baseline. Change in symptoms and relief of pain will be quantified based on subjective completion of validated questionnaires. Data from the questionnaires will provide a reliable assessment of symptomatic relief from the foot ailments being evaluated.

Secondary Endpoint

The secondary endpoint is the change in foot morphology when shoe inserts are worn. The change to be documented is the acute change that occurs in the boney structure of the foot when it is supported with the orthosis. A critical part of the analysis is to demonstrate if there are measurable changes in foot morphology when supported, and to determine if those changes correlate with symptomatic changes in the study subject's foot condition.

Remuneration

Study subjects will not be paid to participate in this study. However, all participants will receive new orthoses and new shoes, and will be permitted to keep these items at the conclusion of the study. Also, all study participants will receive up to \$50 to reimburse them for any travel expenses related to the study. We would like to pay the participants by check on the date of their visit, if permitted to do so.

Sharing of Data and Confidentiality

All data will be kept within the confines of MGH. Since there are no other sites involved in the study, no outside investigators will have a need for access to the data.

7. Risks and Discomforts

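### Two of the seven named X-ray measures are slopes of a single bone, so tested one at a time they can show tilt of the whole foot on the insert as change between bones

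*Combined protocol and SAP*

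**What the plan says.** Specific Aim #1 in Section 2 is to "Measure any changes that occur in the position and alignment of the foot bones relative to one another", with and without the supports. The secondary endpoint in Section 6 is change in foot morphology, described as "the acute change that occurs in the boney structure of the foot when it is supported with the orthosis". Both concern the shape of the foot. The hypothesis under Aim 1 is looser: "Arch supports (orthoses) will alter the positioning and alignment of the bones of the foot when standing".

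Under Baseline Measurements in Section 6a, each subject has one set of images "taken barefooted and a second series taken with the selected arch support in place". The film measures are introduced with "X-ray measurements will include intermetatarsal angles, hallux abductus angle, sesamoid position" and continue with "metatarsal declination angle, calcaneal inclination angle, talocalcaneal angle, calcaneocuboid angle, and overall morphology". That makes seven named measures plus an overall description. For CT, "CT measurements will be used to determine the 3-dimensional positioning of the foot bones".

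No reference line is given for any angle. The text does not say whether the line on the with-support film is the floor or the surface of the support. No coordinate frame is given for CT. Section 9 compares the parameters with and without insoles at a significance level of 0.05 and attaches a Cohen's d to each variable as a guide to practical relevance. It does not mention tilt of the whole foot and does not say which measures answer Aim 1.

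**The concern.** Five of the seven named film measures (intermetatarsal, hallux abductus, sesamoid position, talocalcaneal, calcaneocuboid) conventionally describe one bone against another. Calcaneal inclination and metatarsal declination conventionally describe one bone against the surface it stands on. That surface is exactly what changes between the two films.

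If the support raises the heel more than the forefoot, the foot can rotate as a block. Each slope then changes although no bone has moved against its neighbour. Because each parameter is tested separately, such a change could be reported as structural. In the other direction, a heel-up tilt could offset a real rise in calcaneal inclination, and a true effect would go unseen on that measure.

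**Working it through.** The plan states no effect size, SD or power for the imaging measures, so there is no figure of its own to reproduce. The check is geometric, followed by a size estimate under stated assumptions.

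**Inputs from the protocol:** 50 subjects, single arm (Sections 3 and 4); within-subject contrast of barefoot against support in place (Section 6a); alpha 0.05 (Section 9), taken as two-sided.

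**Assumed, not in the documents:** both slopes are measured to the floor on both films; net heel-over-forefoot height 3 to 10 mm; 180 mm from heel to metatarsal heads; SD of within-subject differences 2 to 4 degrees; starting angles for illustration only.

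**1. Rigid tilt.** Let calcaneal inclination be a, first-metatarsal declination b, and heel-up tilt t. After the tilt, inclination is a − t and declination is b + t. The sum a + b is unchanged, and so is the calcaneal-first metatarsal angle, 180 − (a + b).

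With a = 20, b = 22 and talocalcaneal angle 45 degrees:

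| Tilt (degrees) | Inclination | Declination | Talocalcaneal | Sum |
|---|---|---|---|---|
| 0 | 20 | 22 | 45 | 42 |
| 2 | 18 | 24 | 45 | 42 |
| 5 | 15 | 27 | 45 | 42 |

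**2. Masking.** If the support truly raises inclination by u and declination by v, the observed changes are u − t and v + t. With u = t = 2 degrees, inclination shows no change. The sum shows u + v, free of t.

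**3. Size of tilt.** t = arctan(h/180): h = 3 mm gives 0.95 degrees, 5 mm gives 1.59, and 10 mm gives 3.18.

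**4. Chance of p<0.05 from tilt alone.** This is a paired t-test with n = 50, which equals a two-condition repeated measures ANOVA. Standardised difference d = t/SD, noncentrality d√50, 49 degrees of freedom:

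| Tilt | SD 2 | SD 3 | SD 4 |
|---|---|---|---|
| 1 degree | 93% | 64% | 41% |
| 2 degrees | over 99% | 99.6% | 93% |

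If Cohen's d uses the SD of differences, a 2-degree tilt with SD 3 gives 2/3 = 0.67, which Section 9 would class as moderate.

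**5. Does the sum remove it?** In 20,000 simulated trials of 50 subjects with tilt of mean 2 and SD 1 degree, no movement between bones, and measurement-difference SDs of 1 to 3 degrees, each slope was significant in 99 to 100% of trials. The sum was significant in 4.7 to 5.0%, the nominal rate.

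**6. Correlation with symptoms.** Adding the same constant to every subject's change leaves its correlation with symptom change unaltered. Only tilt that varies between subjects can alter it.

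**The case against.** The strongest reply is that the information needed is already being collected. Rigid heel-up tilt moves the two slopes in opposite directions, while an arch lift raises both. A reader might infer that the listed angles cannot tell the two apart. Read as a pair they can, and the proposed angle is only their sum in another form. That stands. What is missing is a pre-stated variable or rule that reads them together; Section 9 takes parameters one by one.

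A reader might also infer that Aim 1 would be declared met on a tilt. The protocol contains no rule that significance on one or two angles settles Aim 1. Five other film measures and CT bear on it.

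It can further be said that the hypothesis under Aim 1 and the study title speak of position, which a slope to the ground does describe. That is fair and is a reason to keep reporting the slopes. It does not make them evidence on the aim as worded, or on the endpoint, where "The change to be documented is the acute change that occurs in the boney structure of the foot".

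Finally, the ground reference is conventional usage and not protocol text, and nothing shows that this support acts as a heel wedge. Both points stand. If the line were drawn along a support surface that tilts with the foot, a rigid tilt would drop out. That is why the reference line has to be stated.

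**Conclusion.** The concern holds in a limited form. As planned, either slope taken alone can register a change with no movement between bones, and calcaneal inclination can hide a real one. Under the assumed tilts of 1 to 2 degrees and SDs of 2 to 4 degrees, a false structural signal on a single slope would appear in 41% to over 99% of trials of 50. The geometry is exact for a rigid tilt measured to the floor. The amount of tilt, the SDs and the reference line are assumptions, so the percentages illustrate the risk and do not predict it.

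The documents do not support going further. They do not show that the insert tilts the foot. Aim 1 remains answerable from the bone-to-bone angles, and from CT if positions are expressed relative to a bone. It would also be tempting to say that the structure-symptom correlation is compromised. That follows only if tilt differs between subjects, on which the documents are silent. The point affects two component measures of a secondary endpoint and is worth settling before the images are read.

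**What to change.** In Section 6a:

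- State the reference line for each angle on both the barefoot and the with-support film.
- Specify metatarsal declination as first-metatarsal declination; the current text does not say which metatarsal.
- Add the calcaneal-first metatarsal angle, 180 − (calcaneal inclination + first-metatarsal declination), as the lateral-film measure for Aim 1, alongside the other bone-to-bone angles.
- Express CT positions relative to a named reference bone, such as the talus or calcaneus.
- Keep reporting the two slopes, labelled as foot posture relative to the support and not as stand-alone evidence of change between bones.

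The cost is a wording change and one derived variable from films already planned, with no extra imaging. Two familiar angles no longer count alone as evidence for Aim 1. The derived angle is also noisier: with independent errors of equal SD s in the two slopes, its SD is √2 × s, so 3 degrees becomes 4.2. A true arch lift that raises both slopes adds in the sum, which offsets some or all of that loss.

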The study is a minimal risk study, with all subjects receiving the arch supports being investigated. There is no placebo offered. Initial evaluation of all subjects will include all imaging and measurements. Collection of subjective responses will occur after 4 weeks, 8 weeks, and 12 weeks of treatment.

4. Subject Selection

A total of 50 subjects will be enrolled. Subjects must meet the following inclusion and exclusion criteria:

Inclusion

1. Men or women ≥ 18 and ≤ 65 years of age

2. The subject is able and willing to comply with study procedures and a signed and dated informed consent is obtained
3. Subjects diagnosed with symptomatic hallux valgus and/or plantar fasciitis and/or metatarsalgia.
4. Patient has had foot pain for at least 30 days.
5. Willing and able to utilize insole when walking for 90 days.
6. BMI \leq 35
7. Able to walk up to 0.5 miles without difficulty, in a 24-hour period.

Exclusion

1. Inability or unwillingness to comply with study procedures
2. Gross asymmetry in feet, where shoe size differs by 2 or more full sizes between right and left foot
3. Subject has had a CT performed within the last 30 days, for any body part.
4. Prior partial or total amputation of a foot
5. BMI $<$ 35.
6. Unilateral or bilateral foot deformity that would hinder the fitting of an over-the-counter arch support, such as active Charcot foot or Charcot with boney prominence
7. Ulcers or open sores on either foot
8. Currently wearing custom shoes or insoles.
9. Currently ambulating with a cane, crutches, walker.
10. Currently using any type of foot or ankle brace, and/or having used a brace in the last 30 days.
11. Pregnancy

Subject Recruitment:

Subjects will be recruited from the clinicians in the Division of Podiatry under the Department of Orthopaedics. Additionally, the sponsor, Good Feet Worldwide has a trade store the MGH service area, and will allow us to promote the study at their location with an advertisement poster. Potential subjects from the trade store will be referred to our clinics for screening and, when appropriate, recruited for the study.

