The risks include discomfort during walking and/or standing, and can include bruise and/or blister formation, exacerbation of existing foot pain, tightness in shoes, temporary foot or leg cramps, bruising of the foot. X-rays and CT scans will be taken, and these tests involve very low levels of radiation. All of the devices being used in this study are currently available for purchase without a prescription, and are being used in the manner in which they were intended.

There are no new applications being explored for either the insoles or shoes that the study subjects will receive during this study. There are no unusual or excessive risks to study subjects, and all procedures being performed on subjects are already in use for diagnostic and treatment purposes.

8. Benefits

Historically, when these conditions (plantar fasciitis, hallux valgus, metatarsalgia) are treated with arch supports, they have responded with significantly less pain, and in many cases, helped the subjects to avoid surgical correction. We expect that the subjects who participate in this study will show signs of improvement in symptoms. They will also benefit from a highly focused medical examination of their

feet. Future patients will benefit from this study by knowing that arch supports are a safe and effective treatment for these foot ailments. The study may also help to optimize arch support design in the future.

9. Statistical Analysis

Statistical plan is for a one-way repeated measures ANOVA to compare the parameters with participants with and without arch-support insoles for each slope. We anticipate using SPSS for Windows (SPSS Science Inc., Chicago, IL, USA) for the statistical analyses. Levene's test will be used to test the homogeneity of the variances. A Kolmogorov-Smirnov test will be used to evaluate the normality of the data, a Wilcoxon test will be used when the data are not normally distributed. The significance level was set at $\alpha = 0.05$. The effect size (ES) for the difference from baseline will be calculated for each variable as a measure of the practical relevance of the significance using Cohen's d ; ES values between 0.20 and 0.49 are considered small, those between 0.50 and 0.79 are considered moderate, and those 0.80 and above are considered large.

10. Monitoring and Quality Assurance

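### No questionnaire is required at or after withdrawal and the named ANOVA needs every visit, so the single-arm result rests on completers and could overstate improvement

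*Combined protocol and SAP*

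**What the plan says.** The protocol describes the design in Section 3: "This study is a single armed prospective case series designed to evaluate the efficacy of treating common structural-related foot ailments". Section 4 states: "A total of 50 subjects will be enrolled". The primary endpoint, in Section 6c, is questionnaire-based symptom change from baseline while the supports are in use.

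On leaving the study, Section 6c says: "In all cases of withdrawal, the date and the reason for withdrawal are to be documented". It also asks for relevant information on the device and the subject's condition. Subjects withdrawn for an adverse event are followed until it resolves, returns to baseline or is no longer expected to resolve. The paragraph on treatment discontinuation deals only with completing the study and withdrawing from it. It does not address a subject who stops wearing the supports but remains enrolled.

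On collection, Section 6b says: "We will be conducting follow up surveys via email and RedCap links with patients". The questionnaires are due at the three follow-up visits, and a weekly diary records pain and wear.

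On analysis, Section 9 names a "one-way repeated measures ANOVA", a Wilcoxon test for non-normal data, and Cohen's d: "The effect size (ES) for the difference from baseline will be calculated for each variable". It defines no analysis population, missing-data method or sensitivity analysis. Section 7 lists "exacerbation of existing foot pain" among the risks.

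**The concern.** The protocol itself foresees that the device may worsen pain, and subjects whose pain worsens have an obvious reason to stop. If they leave, no later questionnaire is required of them. If they lack even one visit, a classical repeated measures ANOVA drops them altogether, including any week 4 or week 8 scores already given.

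In a two-arm trial, part of such loss may be shared between the arms. Here the estimate is a within-subject change with nothing to compare it against, so any selective loss enters the mean change, Cohen's d and the p-value directly. Scores that were never collected cannot be recovered at the analysis stage.

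**Working it through.** **Inputs from the protocol.** Single arm, 50 subjects, scores at weeks 0, 4, 8 and 12, alpha 0.05 (sidedness not stated; two-sided assumed), and Cohen's d bands starting at 0.20, 0.50 and 0.80.

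**Inputs not given, so assumed.** Dropout rate, SD, correlations between visits, and the reasons for leaving.

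**The plan's own figure.** The 50 has no stated basis and cannot be reproduced. For orientation, a paired comparison with d = 0.5 and 90% power needs ((1.960 + 1.282)/0.5)² = 42.03, so 43. Allowing 10% dropout gives 43/0.9 = 47.8, so 48. That is close to 50, but the protocol states none of these inputs and no dropout allowance.

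**Step 1: who enters each analysis.**
- Classical repeated measures ANOVA: subjects with all four visits.
- Wilcoxon test and Cohen's d on change: subjects with baseline and the visit in question.
- In neither case does a subject who left before week 12 contribute to the week 12 result.

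**Step 2: simple mixture.** Let q be the fraction lost. Completer mean minus all-subject mean = q × (completer mean − leaver mean). With completers improving by 0.50 SD, the error in the completer figure is:

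| Leavers' mean improvement | q = 10% | q = 20% | q = 30% |
|---|---|---|---|
| −0.50 SD (worse) | +0.10 | +0.20 | +0.30 |
| 0 | +0.05 | +0.10 | +0.15 |
| +0.50 SD (same) | 0 | 0 | 0 |
| +1.0 SD (recovered) | −0.05 | −0.10 | −0.15 |

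When leavers have zero change, the ratio of completer to all-subject mean is 1/(1−q): 0.50/0.45 = 1.11 and 0.50/0.40 = 1.25. This is not an upper limit, because it is larger if leavers worsened.

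**Step 3: simulation, loss driven by observed worsening.** Assumed: a 0–100 scale (lower is better), SD 20, correlation 0.5 between baseline and follow-up and 0.8 between follow-ups, and logistic stopping after weeks 4 and 8 on the observed change (slope 1 per SD). The SD of change is 20 × √(2 × (1 − 0.5)) = 20, so a true change of −10 is d = 0.5.

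| Loss | Completer estimate, true −10 | Likelihood model, all visits | Completer type I error, true 0 |
|---|---|---|---|
| 11% | about −11.6 | about −10 | about 8% |
| 18% | about −12.5 | about −10 | about 14% |

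On the SD of 20, the completer estimates are d = 11.6/20 = 0.58 and 12.5/20 = 0.63. Repeat runs gave −11.5 to −11.7 and −12.5 to −12.8. With a steeper link (slope up to 1.5 per SD) and 21% to 22% loss, type I error was 26% to 29%. With loss unrelated to outcome it stayed near 5%, with no bias.

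**Step 4: a different loss model.** Dropout was driven by a latent score correlated 0.5 with improvement, and the true change was zero. A completer-only t-test then declared improvement in 10%, 21% and 33% of trials at 10%, 20% and 30% dropout, against a nominal 2.5%. Apparent d was 0.10, 0.19 and 0.27, so the last reaches the protocol's small band with no real effect. With the correlation reversed to −0.5, apparent d was −0.10, −0.18 and −0.27.

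**Step 5: what a mixed model cannot repair.** Here loss depends on the current score before it is recorded, at all three visits. For a true −10:
- 11% loss: completers −12.0, likelihood model −10.9. Bias removed (12.0 − 10.9)/(12.0 − 10) = 55%.
- 19% loss: completers −14.1, likelihood model −11.8. Bias removed (14.1 − 11.8)/(14.1 − 10) = 56%.

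The near-exact recovery in Step 3 is therefore a best case.

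**The case against.** The strongest reply is that the protocol is silent rather than wrong. Follow-up questionnaires are due at every visit, with no condition that the supports are still worn, and the diary tracks wear, which suggests that non-wearers may stay in. Section 9 states no complete-case rule. Its ANOVA sentence speaks of conditions with and without insoles and of slopes, so it may not have been written for the week 4 to 12 questionnaires at all. The Wilcoxon test and Cohen's d can be computed visit by visit from available pairs, and early leavers may have diary pain scores.

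Much of this stands. A reader might infer that everyone who stops the supports leaves the study, or that nothing but a date and reason is kept. The documents support neither. Section 6c also collects device and condition information and follows adverse events, although that is safety follow-up and does not supply the endpoint.

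The gap remains, however. The ANOVA is the only model named, per-visit pairs still omit whoever has left, and the diary is given no role in handling missing data. Section 6b also asks for eligibility to be reconfirmed monthly, and the Section 4 criteria include willingness and ability to use the insole for 90 days. The consequence of failing that check is not stated, which adds to the uncertainty about who stays in.

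**Conclusion.** The point holds as a correctable weakness. As written, the questionnaire result would rest on subjects with complete data, or with data at the visit analysed, and no outcome is required from those who leave. If people leave because the supports hurt, improvement could be overstated. In the main illustration that is about 1.6 points at 11% loss and 2.5 at 18%, on a true change of 10, with type I error of about 8% and 14%.

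A reader might go further and conclude that improvement will be overstated. The documents do not support that, because they give no dropout rate, SD or mix of reasons. The bias is zero if loss is unrelated to outcome and reverses if recovered subjects leave. Every size above depends on assumed inputs.

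**What to change.** 1. **Section 9.** For the questionnaire endpoint, replace the repeated measures ANOVA with a mixed model for repeated measures in all subjects who received supports, using every available visit. Including baseline as one of the modelled visits keeps subjects who leave before week 4 in the analysis.
2. **Section 6c.** Separate stopping the supports from leaving the study. Unless consent is withdrawn, keep sending the existing RedCap questionnaires at weeks 4, 8 and 12, collect one set at exit, and record at each whether the supports are still worn.
3. **Primary endpoint.** State whether scores given after stopping count. The present wording ties the endpoint to wearing the supports, so pooling off-device scores without saying so would answer a different question. Report the other version as a sensitivity analysis.
4. **Sensitivity to unobserved worsening.** The mixed model corrects only for loss explained by recorded scores. Add an analysis that sets subjects who left for device discomfort first to no change and then to worsening by an amount fixed in advance.

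The cost is a few sentences in Sections 6c and 9, some reminder emails, and possibly a smaller estimated effect. The email and RedCap route already exists, and the decision to stop wearing the device is unaffected.
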